12.5.2 Secondary Analyses

12.5.2.1 VAS Craving score

At Day 30, an analysis of covariance (ANCOVA) will be performed on the AUC for the VAS craving score over the duration 0-4h post T₀ denoted AUC_{VAS Craving (0-4h)}. The model will have P3P variant and sex as factors and Day 1 value as covariate. Comparisons between variants will be performed and LSmeans differences between variant reported with their 95% CI. LSMeans and 95% CI for the AUC_{VAS Craving (0-4h)} by variant will also be reported.

Changes from baseline at Day 30 in AUC_{VAS Craving (0-4h)} will also be analyzed in an ANOVA model with variant and sex as factors. Within-group changes from baseline will be estimated using LSMeans and 95% CI.

Descriptive Statistics of AUC_{VAS Craving (0-4h)} at Day 1 and Day 30 and Change from Day 1 at Day 30 Overall; By Sex and By Exposure Category will be provided.

VAS craving score at Day 1 and Day 30 and changes from Day 1 value will be summarized in a descriptive manner by timepoint and P3P variant.

TFL number	Title
TABLES	
15.2.13.1	Descriptive Statistics of AUC _{VAS Craving (0-4h)} at Day 1 and Day 30 and Change from Day 1 at Day 30 – Randomized Population
15.2.13.2	Analysis of AUC _{VAS Craving (0-4h)} at Day 1 and Day 30 and Change from Day 1 at Day 30 – Randomized Population
15.2.13.3	Descriptive Statistics of AUC _{VAS Craving (0-4h)} at Day 1 and Day 30 and Change from Day 1 at Day 30 – By Sex - Randomized Population
15.2.13.4	Descriptive Statistics of AUC _{VAS Craving (0-4h)} at Day 1 and Day 30 and Change from Day 1 at Day 30 – By Product Exposure Category - Randomized Population
15.2.13.5	Descriptive Statistics of VAS craving score at Day 1 and Day 30 and Change from Day 1 at Day 30 by Timepoint – Randomized Population
15.2.13.6	Descriptive Statistics of VAS craving score at Day 1 and Day 30 and Change from Day 1 at Day 30 by Timepoint by Sex – Randomized Population
15.2.13.7	Descriptive Statistics of VAS craving score at Day 1 and Day 30 and Change from Day 1 at Day 30 by Timepoint by Product Exposure Category – Randomized Population
FIGURES	
15.3.3.1	VAS Craving Score Profiles By Timepoint at Day 1 and Day 30 – Randomized Population
15.3.3.2	Individual VAS profiles – Randomized Population

TFL number	Title
LISTINGS	
15.1.13.1	Listing of AUCVAS Craving (0-4h)
15.1.13.2	Listing of VAS craving scores

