#### 12.1.2 Definitions for Statistical Data Analysis

For plasma nicotine time-concentration and VAS-craving, baseline will be defined as the last measurement prior to product use for PK assessment (prior to T0)

For the changes from baseline in PK parameters, PD parameters, CYP2A6 and product acceptance, described in sections 3.1 and 3.2, Day 1 value will be considered as the baseline. For BoExp and safety parameters the last assessments prior to product test will be considered as baseline.

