## 12.6 Secondary Objectives and Endpoints

### 12.6.1 Secondary Endpoint Analysis Variables

#### 12.6.1.1 PD endpoints

PD endpoints are listed in section [3.2](#).

VAS craving score and changes from baseline will be summarized by timepoint. In addition, AUCVAS will be derived by P3P variant: AUCVAS (0-4h).

Sensory Questionnaire and ABOUT Product Experience Questionnaire will be described as detailed in section [12.1.3](#). Further details on the summary statistics of these questionnaires will be provided in the SAP.

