7.2 Pharmacodynamic effects

7.2.1 Visual Analogue Scale for Craving

A VAS-craving assessment will be used to assess the level of craving of the subject based on their response to the question, "How strong is your craving for cigarettes?" on a scale of 0 (no craving) to 10 (strong craving).

The VAS craving will be completed multiple times by the subject in relation to the P3P product used for PK assessment at Day 1 and Day 30. The first assessment will be done 10 minutes \pm 2 minutes prior to T_0 . Thereafter in relation to T_0 , the assessment is to be performed at 4 minutes \pm 2 minutes, at 10 minutes \pm 2 minutes, at 15 minutes \pm 2 minutes, 30 minutes \pm 5 minutes, 1 hour \pm 10 minutes, 2 hours \pm 10 minutes and 4 hours \pm 10 minutes. VAS will be assessed immediately after the collection of the time-matching PK samples.

For Day 1 and Day 30, baseline VAS-craving is defined as the measurement obtained at 10 \pm 2 min prior to the T_0 at Day 1 and Day 30, respectively.

Baseline for this endpoint is therefore different at Day 1 and Day 30.

VAS craving score and changes from baseline will be summarized by timepoint within Day 1 and Day 30. In addition, at Day 1 and Day 30, $AUC_{VAS(0-4)}$ will be derived using the linear trapezoidal method. For the calculations of $AUC_{VAS(0-4)}$, the actual timepoints of VAS

assessments instead of nominal timepoint will be used. The first VAS value to be taken into account in the derivation of $AUC_{(0-4)}$ is the value obtained 10 min prior to the T_0 timepoint, which will be considered as value at T_0 . The last value being the last measurement performed at the 4h post T_0 timepoint.

If the 4h post T_0 timepoint is missing, the $AUC_{VAS(0-4)}$ will be set to missing.

If the 4h post T_0 timepoint is collected after 3h but prior to 3h50 post T_0 , the 4h post T_0 the score will be derived using the extrapolation at 4h based on the last 2 timepoints collected prior to 4h.

If the 4h post T_0 timepoint is collected after 4h10 but prior to 5h post T_0 , the 4h post T_0 score will be interpolated between the last 2 timepoints.

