12.1.4 Definitions of Baseline for Statistical Data Analysis

Baseline values for pharmacodynamic parameters (VAS Craving, Sensory Questionnaire, ABOUT™-Product experience), Product Acceptance, ABOUT™-Dependence, and Puffing/Inhalation behavior questions are defined in section 7.1, 7.2.1, 7.2.2, 7.2.3, 7.3.1, 7.5.1 and 7.3.2 respectively.

Baseline values of BoExp will be defined as the value measured on V2 (Day -1) when spot urine should be collected prior to product test. Baseline for CYP2A6 will be defined as the value determined on Day 1, see section 7.6.

For safety parameters the last assessment prior to product test at Day -1 will be considered as baseline.

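### The change from same-day pre-use craving promised in SAP 7.2.1 has no listed table and no model in SAP 12.5.2.1, so the within-variant Day 30 versus Day 1 AUC-VAS result cannot separate acute effect from a shift in pre-use craving

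*SAP*

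**What the plan says.** The documents use two reference points for craving.

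**Same-day pre-use score.**
- Protocol 12.1.2: "For plasma nicotine time-concentration and VAS-craving, baseline will be defined as the last measurement prior to product use for PK assessment".
- Protocol 12.6.1.1: "VAS craving score and changes from baseline will be summarized by timepoint".
- SAP 7.2.1 takes the score 10 ± 2 minutes before T0 on each PK day, notes that "Baseline for this endpoint is therefore different at Day 1 and Day 30", and plans that "VAS craving score and changes from baseline will be summarized by timepoint within Day 1 and Day 30".
- SAP 12.1.4 sends the reader back to 7.2.1 for this baseline.

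**Day 1.** The second paragraph of protocol 12.1.2 makes the Day 1 value the baseline for change in PD parameters.

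SAP 12.5.2.1, which sets out the analyses and lists the tables, uses only the second:
- By timepoint: "VAS craving score at Day 1 and Day 30 and changes from Day 1 value will be summarized".
- Between variants: an ANCOVA of raw AUC-VAS(0-4h) at Day 30, with variant and sex as factors and the Day 1 value as covariate.
- Within variant: an ANOVA of change in AUC-VAS. The text says change from baseline, and the table titles show that this means Day 1.
- The titles of tables 15.2.13.1 to 15.2.13.7 name raw values and, for change, only change from Day 1.

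SAP section 9, which records departures from the protocol, does not mention dropping same-day change.

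**The concern.** Secondary objective 1 concerns the pharmacodynamic effects of the two variants, and craving is measured around a single product use in parallel with PK sampling. Two quantities are of interest: how much craving falls after one product, and how strong craving is overall on each day.

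The VAS item asks about craving for cigarettes. Day 1 comes just after habitual smoking. Day 30 comes after a month in which subjects were told to use P3P exclusively. Pre-use craving could well differ between the two days even if one product does exactly the same thing on both. Raw AUC-VAS would then change, and a reader could take this as a change in craving relief. Table 15.2.13.2, which holds the AUC-VAS models, is in the topline set (SAP 13.2), so this result will be among the first seen.

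**Working it through.** The documents give no craving mean, SD or effect size, and the sample size is empirical. There is therefore no planned figure to reproduce. The check is how AUC-VAS, as defined, responds to a level shift.

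**Inputs from SAP 7.2.1.** The scale runs from 0 to 10. Scores are at T0 (the pre-use score placed at T0) and at 4, 10, 15, 30, 60, 120 and 240 minutes. The rule is the linear trapezoid.

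**Step 1: weight of each score.** An interior point has weight (next time − previous time)/2; an end point has half its adjacent interval.

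| Time (min) | 0 | 4 | 10 | 15 | 30 | 60 | 120 | 240 |
|---|---|---|---|---|---|---|---|---|
| Weight (h) | 0.033 | 0.083 | 0.092 | 0.167 | 0.375 | 0.750 | 1.500 | 1.000 |

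The weights sum to 4 h. The pre-use score carries 0.033/4 = 0.83% of the weight. Its presence in the AUC does not act as a baseline correction.

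**Step 2: effect of a uniform shift.** If every score on Day 30 is d points away from its Day 1 value, the change in raw AUC is d × 4 h.
- d = 0.5: 2 point-hours
- d = 1: 4
- d = 2: 8
- d = 3: 12

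The maximum possible AUC is 10 × 4 = 40 point-hours, so d = 1 is 4/40 = 10% of the range. The values of d are assumptions.

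**Step 3: compare with a real change in acute effect.** Assume drops from the pre-use score of 0, 0.5, 1, 1.5, 2, 1.5, 1 and 0 points at the eight times. The weighted sum is

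0.083×0.5 + 0.092×1 + 0.167×1.5 + 0.375×2 + 0.75×1.5 + 1.5×1 = 3.76 point-hours.

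With pre-use craving of 7 on Day 1, raw AUC is 7×4 − 3.76 = 24.24.

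| Day 30 scenario | Change in raw AUC | Change in same-day-corrected AUC |
|---|---|---|
| Pre-use 7, same drops | 0 | 0 |
| Pre-use 6, same drops | −4 | 0 |
| Pre-use 5, same drops | −8 | 0 |
| Pre-use 4, same drops | −12 | 0 |
| Pre-use 7, drops doubled | −3.76 | −3.76 |

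Under this profile, a 1-point background shift and a doubling of the acute effect give nearly the same raw result (−4 and −3.76). The corrected AUC, which is raw AUC − 4 × the same-day pre-use score, separates them.

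**Step 4: does the Day 1 covariate help?** The ANCOVA covariate is the Day 1 AUC. A shift that arises after Day 1 is not contained in it, so adjustment cannot remove it. The within-variant ANOVA models the Day 30 minus Day 1 difference directly and carries the full 4d. In the between-variant contrast, a shift common to both variants cancels; shifts that differ by δ points contribute 4δ.

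**The case against.** The case against acting has several parts.

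- **Same-day change is planned.** SAP 7.2.1 says so. A reader who sees only 12.5.2.1 might infer that the plan never looks at it; 7.2.1 and protocol 12.6.1.1 rule that out. What is missing is any listed output or model that delivers it.
- **Day 1 is a proper baseline.** Protocol 12.1.2 names it for PD parameters, so change from Day 1 in AUC-VAS follows the protocol. This stands. It does not replace the other baseline in the same section.
- **Titles are not table contents.** SAP section 3 leaves detail to a separate shell document, and SAP 12.1.3 adds change from baseline where applicable. The shells may contain the missing columns. However, SAP 13.3 says the tables to be presented are listed in the SAP sections, and the text of 12.5.2.1 specifies change from Day 1.
- **The shift would be visible.** Tables 15.2.13.5 to 15.2.13.7, figures 15.3.3.1 and 15.3.3.2 and listing 15.1.13.2 should show pre-use levels. This largely stands, but none is titled as giving an estimate or interval for same-day change.
- **Craving reduction is also measured elsewhere.** The ABOUT-Product Experience questionnaire has a single craving-reduction item after the PK product on both days, with models by subscale in SAP 12.5.2.3. It is useful support, but it is a retrospective rating and not the VAS endpoint.
- **Total craving is a fair target.** For a study of one-month adaptation, overall 4-hour craving is a reasonable outcome. This stands, and is why raw AUC should be kept.

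It is also tempting to argue that craving must be corrected because nicotine concentrations are. That does not follow. The PK correction removes residual nicotine left by a limited washout; pre-use craving is not drug carry-over.

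**Conclusion.** The point holds as an inconsistency with a consequence for interpretation. SAP 7.2.1 and both protocol sections promise change from the same-day pre-use score; SAP 12.5.2.1 provides no listed table and no model for it, and section 9 does not record its removal.

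The consequence falls on the within-variant Day 30 versus Day 1 AUC-VAS estimate. It moves by 4 point-hours for each point of uniform shift in craving level, so 2 to 12 point-hours over the assumed 0.5 to 3 points, whether or not the product's acute effect has changed. The multiplier follows from the SAP's nominal times. The size of any shift, and the acute profile used for comparison, are assumptions, and no expected variability is given against which to judge them.

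A reader might go further and infer that the between-variant craving comparison is invalid. The documents do not support that: at Day 30 it remains a randomized comparison of total 4-hour craving, and it mixes the two components only if pre-use shifts differ by variant. Nor do they show that a shift will occur. The study is described as descriptive, with no claim to rest on individual intervals (SAP 5.3.1 and 12.1.6), which limits the stakes but does not settle what the estimate means.

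**What to change.** In SAP 12.5.2.1:

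1. Add change from the same-day pre-T0 score, by timepoint and variant, to tables 15.2.13.5 to 15.2.13.7.
2. Add, as a supportive analysis, AUC(0-4h) of change from the same-day pre-T0 score at Day 1 and Day 30, with the same ANCOVA and ANOVA as for raw AUC-VAS. The Day 1 value of the corrected AUC would be the ANCOVA covariate.
3. Name the two baselines distinctly throughout, for instance same-day pre-use and Day 1, and replace the unqualified word baseline in the AUC-VAS change model.
4. Keep raw AUC-VAS as planned.

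No new data are needed. The work is SAP wording, extra columns and one additional analysis. The downside is one more secondary estimate, which may be noisier because it subtracts a single pre-use score; the documents do not allow that loss to be calculated.

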12.5.2.2 Sensory Questionnaire

Descriptive statistics for the 8 items of the questionnaire on a 7-point scale will be provided by group at Day 1 and Day 30. Data will not be reported by category; this data on a 7-point scale will be considered continuous.

TFL number	Title
TABLES	
15.2.14.1	Descriptive Statistics of Each Item of Sensory Questionnaire (Day 1 and Day 30 and Change from Day 1 at Day 30) (By Variant and Total) – Randomized Population
15.2.14.2	Descriptive Statistics of Each Item of Sensory Questionnaire by Timepoint (Day 1 and Day 30 and Change from Day 1 at Day 30) – By Sex - Randomized Population
15.2.14.3	Descriptive Statistics of Each Item of Sensory Questionnaire (Day 1 and Day 30 and Change from Day 1 at Day 30) – By Product Exposure Category - Randomized Population
LISTINGS	
15.1.14.1	Listing of Sensory Questionnaire Results

12.5.2.3 ABOUTTM-Product Experience Questionnaire

The questionnaire which consists of multi-item scales and two single-item scales will be listed and summarized by variant and by stratification factor (sex) for the PK populations.

At Day 30, an ANCOVA model will be used to estimate the mean P3P-2mg:P3P-1mg difference by subscale of the ABOUTTM-Product Experience Questionnaire; the model will include P3P variant and sex as factors and value of the subscale score at Day 1 as covariate.

LS means for each variant with 95% interval estimate will be presented in the tables together with the LS mean between-variant difference and 95% confidence interval.

Within-group comparisons between Day 30 and Day 1 will be performed on the basis of an ANOVA model with sex and product exposure category as factors.

The data will be presented in the below outputs:

TFL number	Title
TABLES	
15.2.15.1	Descriptive Statistics of ABOUT™-Product Experience Questionnaire Subscales at Day 1 and Day 30 and Change from Day 1 at Day 30 - Randomized Population
15.2.15.2	Analysis of ABOUT™ Product Experience Questionnaire Subscales at Day 30 and Change from Day 1 at Day 30 - Randomized Population
15.2.15.3	Descriptive Statistics of ABOUT™ Product Experience Questionnaire Subscales at Day 1 and Day 30 and Change From Day 1 at Day 30 by Sex – Randomized Population
15.2.15.4	Descriptive Statistics of ABOUT™ Product Experience Questionnaire Subscales at Day 1 and Day 30 and Change From Day 1 at Day 30 by Product Exposure Category – Randomized Population
15.2.15.5	Descriptive Statistics of ABOUT™ Product Experience Questionnaire Individual Questions at Day 1 and Day 30 and Change from Day 1 at Day 30 – Randomized Population
LISTINGS	
15.1.15.1	Listing of ABOUT™ Product Experience Questionnaire Results

12.5.3 Product acceptance and puffing/inhalation behavior

12.5.3.1 Product Acceptance Questionnaire

The data will be presented in the below outputs in a descriptive manner:

Answers to questions 1 to 4 will be considered continuous while answers to questions 5 and 6 will be presented using frequencies.

TFL number	Title
TABLES	
15.2.16.1	Descriptive Statistics of Product Acceptance at Day 1 and Day 30 and Change from Day 1 at Day 30 (Questions 1 to 4)– Randomized Population
15.2.16.2	Descriptive Statistics of Product Acceptance at Day 1 and Day 30 (Question 5 and 6)– Randomized Population
15.2.16.3	Descriptive Statistics of Product Acceptance (Question 5) – Shift Table from Day 1 to Day 30– Randomized Population
15.2.16.4	Descriptive Statistics of Product Acceptance at Day 1 and Day 30 and Change from Day 1 at Day 30 (Questions 1 to 4) – By Sex - Randomized Population

TFL number	Title
15.2.16.5.	Descriptive Statistics of Product Acceptance at Day 1 and Day 30 (Question 5 to 6)– By Sex- Randomized Population
15.2.16.6	Descriptive Statistics of Product Acceptance at Day 1 and Day 30 and Change from Day 1 at Day 30 (Questions 1 to 4) – By Product Exposure Category- Randomized Population
15.2.16.7	Descriptive Statistics of Product Acceptance at Day 1 and Day 30 (Question 5 to 6) – By Product Exposure Category- Randomized Population
LISTINGS	
15.1.16.1	Listing of Product Acceptance Results

12.5.3.2 Puffing/Inhalation behavior

Descriptive data will be presented in the below outputs:

TFL number	Title
TABLES	
15.2.17.1	Descriptive Statistics of Puffing Inhalation Behavior Evaluated By Site Staff at Day 1 and Day 30 – Randomized Population
15.2.17.2	Descriptive Statistics of Puffing Inhalation Behavior Evaluated By Site Staff - Shift Table From Day 1 to Day 30 – Randomized Population
15.2.17.3	Descriptive Statistics of Puffing Inhalation Behavior Evaluated By Subject at Day 2, Day 7, Day 15, Day 22 and Day 29 – Randomized Population
15.2.17.4	Descriptive Statistics of Puffing Inhalation Behavior Evaluated By Subject - Shift Table From Day 2 to Day 7, Day 15, Day 22 and Day 29 – Randomized Population
15.2.17.5	Descriptive Statistics of Puffing Inhalation Behavior Evaluated By Site Staff at Day 1 and Day 30 - By Product Exposure Category – Randomized Population
15.2.17.6	Descriptive Statistics of Puffing Inhalation Behavior Evaluated By Subject at Day 2, Day 7, Day 15, Day 22 and Day 29 - By Product Exposure Category – Randomized Population
LISTINGS	
15.1.17.1	Listing of Puffing/Inhalation Behavior (Site) Results
15.1.17.2	Listing of Puffing/Inhalation Behavior (Subject) Results

12.5.4 Nicotine/Tobacco product use

The following variables:

- Average Cigarettes smoked per day during a period
- Change from baseline in average number of cigarettes used per day during a period

- Average Heat not burn and/or smokeless tobacco products used per day during a period
- Average Other tobacco products (pipe, cigar, cigarillos, chewable...) used per day during a period
- Average occasions Electronic Cigarette used per day during a period
- Percentage (%) of P3P used during a period with % P3P = $100 * \text{number of P3P} / (\text{number of P3P and CC})$
- Percentage of subjects having used any Nicotine Replacement Therapies during a period

will be summarized in a descriptive manner for each period being the time interval between 2 consecutive visits and also for the complete exposure period.

The data will be presented in the below outputs:

TFL number	Title
TABLES	
15.2.18.1	Descriptive Statistics of Average Cigarettes smoked /day - By Period – Safety Population
15.2.18.2	Descriptive Statistics of Average Cigarettes smoked /day By Product Exposure Category (≤ 5 P3P/day, $> 5 - 10$ P3P/day, > 10 P3P/day) - By Period – Safety Population
15.2.18.3	Descriptive Statistics of Change from Baseline in Average Cigarettes smoked /day - By Period – Safety Population
15.2.18.4	Descriptive Statistics of Average Heat not burn and/or smokeless tobacco products used /day - By Period – Safety Population
15.2.18.5	Descriptive Statistics of Average Other tobacco products (pipe, cigar, cigarillos, chewable...) used/day - By Period – Safety Population
15.2.18.6	Descriptive Statistics of Average occasions Electronic Cigarette used /day - By Period – Safety Population
15.2.18.7	Descriptive Statistics of Percentage (%) of P3P use - By Period – Safety Population
15.2.18.8	Percentage of subjects having used any Nicotine Replacement Therapies – By Period
LISTINGS	
15.1.18.1	Listing of Nicotine/Tobacco product use - By Period

12.5.5 Biomarkers of Exposure in Urine

Urinary concentrations adjusted for creatinine of biomarkers of exposure : Nicotine Equivalents (NEQ), total NNAL and CEMA will be considered log-normally distributed and summarized as described in section 12.1.3. The number and percent of values below LLOQ or above ULOQ will be presented in each summary table.

For each timepoint (Day 7, Day 15, Day 22, Day 29), the values and percent changes from baseline (Day -1) in the concentration adjusted for creatinine of NEQ, total NNAL and CEMA will be summarized by P3P variant, and by product use category.

The data will be presented in the below outputs:

TFL number	Title
TABLES	
15.2.19.1	Descriptive Statistics for Biomarkers of Exposure in Urine and Percent change from baseline - By Timepoint– Randomized Population
15.2.19.2	Descriptive Statistics for Biomarkers of Exposure in Urine and Percent Change from Baseline - By Timepoint – By Product Exposure Category - Randomized Population
15.2.19.3	Descriptive Statistics for Biomarkers of Exposure in Urine and Percent Change from Baseline - By Timepoint – By Sex - Randomized Population
LISTINGS	
15.1.19.1	Listing of Biomarkers of Exposure in Urine – By Timepoint - Results

12.5.6 Tobacco and nicotine containing product dependence

The level of perceived dependence associated with tobacco and nicotine-containing product use, summarized by the total score derived from the ABOUT™- Dependence questionnaire as well as by 3 domain scores will be described.

The individual questions (3c, 3d, 4i, 4j) which are not part of one of the domain scores will only be listed in 15.1.20.1.

The data will be presented in the below outputs:

TFL number	Title
TABLES	
15.2.20.1	Descriptive Statistics of ABOUT™- Dependence questionnaire - Total and By Domain – Baseline, Day 30 and change from baseline – Randomized Population
15.2.20.2	Descriptive Statistics of ABOUT™- Dependence questionnaire – Total and By Domain – Baseline, Day 30 and Change From Baseline at Day 30 - By Product Exposure Category - Randomized Population
LISTINGS	
15.1.20.1	Listing ABOUT™- Dependence questionnaire Results

